11.3.	Guidance for Monitoring Potential Treatment-Related Penile Erections and Suggested Criteria for Discontinuation of Dosing	69
11.4.	Assessment of Renal Function	69
11.4.1.	Modification of Diet in Renal Disease (MDRD) Equation	69
11.4.2.	Bedside Schwartz Equation	69
11.5.	Considerations for Reducing Pain and Distress in the Pediatric Population	69
11.6.	Guidance on Study Conduct During the COVID-19 (Coronavirus) Pandemic	71

LIST OF TABLES

Table 1:	Schedule of Assessments	3	8
----------	-------------------------	---	---

Abbreviation Definition		
Definition		
Anti-drug (i.e., setmelanotide) antibody		
Adverse event		
Alanine transaminase		
Arcuate nucleus of the hypothalamus		
Alström syndrome		
Aspartate transaminase		
Bardet-Biedl syndrome		
Bardet-Biedl syndrome-associated genes		
Body mass index		
Blood pressure		
Beats per minute		
Deuts per minute		
Blood urea nitrogen		
Blood urea nitrogen		
Blood urea nitrogen		
Blood urea nitrogen Code of Federal Regulations		
Blood urea nitrogen Code of Federal Regulations Combined medial hypothalamic lesion		
Blood urea nitrogen Code of Federal Regulations Combined medial hypothalamic lesion Carbon dioxide		
Blood urea nitrogen Code of Federal Regulations Combined medial hypothalamic lesion Carbon dioxide Coronavirus disease 2019		
Blood urea nitrogen Code of Federal Regulations Combined medial hypothalamic lesion Carbon dioxide Coronavirus disease 2019 Creatine phosphokinase		

LIST OF ABBREVIATIONS

Abbreviation	Definition
C-SSRS	Columbia Suicide Severity Rating Scale
CTCAE	Common Terminology Criteria for Adverse Events
DSM-III	Diagnostic and Statistical Manual of Mental Disorders Third Edition
EC ₅₀	Half maximal effective concentration
ECG	Electrocardiogram
eCRF	Electronic case report form
ET	Early termination
FSH	Follicle-stimulating hormone
GCP	Good clinical practice
GFR	Glomerular filtration rate
GGT	Gamma-glutamyl transpeptidase
HbA1c	Glycated hemoglobin
НО	Hypothalamic obesity
HR	Heart rate
IB	Investigator Brochure
ICH	International Council for Harmonisation
IEC	Independent Ethics Committee
IRB	Institutional Review Board
IUD	Intrauterine device
Ki	Inhibitory constant
LDH	Lactate dehydrogenase
LEP	Leptin hormone
LEPR	Leptin receptor
MC4R	Melanocortin-4 receptor
MedDRA	Medical Dictionary for Regulatory Activities
MHP	Mental health professional

Abbreviation	Definition
MSH	Melanocyte stimulating hormone
MTII	Melanotan II
NAFLD	Non-alcoholic fatty liver disease
NASH	Non-alcoholic steatohepatitis
NDA	New Drug Application
NHLBI	National Heart, Lung, and Blood Institute
PCSK1	Proprotein Convertase Subtilisin/Kexin Type 1
РОМС	Pro-opiomelanocortin
PPL	POMC/PCSK1/LEPR
RSI	Reference safety information
SAE	Serious adverse event
SAP	Statistical analysis plan
SC	Subcutaneous
SF-10	10-Item Short Form Health Survey for Children
SH2B1	SH2B Adaptor Protein 1
SMS	Smith-Magenis syndrome
SOA	Schedule of assessments
SRC1	Steroid receptor coactivator-1
T4	Thyroxine
TSH	Thyroid-stimulating hormone
ULN	Upper limit of normal
US	United States
UV	Ultraviolet
VMN	Ventromedial nucleus of the hypothalamus

Abbreviation	Definition
WOCBP	Woman of childbearing potential

1. INTRODUCTION

Rhythm (the sponsor) is focusing the development of setmelanotide as a treatment for patients with rare genetic, syndromic, or acquired diseases of obesity due to specific genetic defects that impact the functioning of the melanocortin-4 receptor (MC4R) pathway, a highly conserved hypothalamic pathway critical for regulation of appetite, energy expenditure, and body weight. The MC4R pathway is the key pathway regulating body weight and appetite. Genetic or acquired defects in the MC4R pathway and other abnormalities of the MC4R pathway cause hyperphagia, an insatiable hunger, leading to severe and early-onset obesity.

The focus of setmelanotide development is on hyperphagia and obesity arising from lack of activation of MC4Rs and lack of "downstream signaling" due to genetic variants or other impairments "upstream" of the MC4R. By activating the MC4R with setmelanotide (a MC4R agonist), signaling occurs in the "downstream" portion of the pathway, and thereby setmelanotide is hypothesized to provide compelling and persistent efficacy on the regulation of appetite and body weight.

Human genetics studies have identified several diseases that are the result of genetic defects affecting the MC4R pathway, for example, syndromes or variants of the following genes:

- Pro-opiomelanocortin (POMC)
- Proprotein Convertase Subtilisin/Kexin Type 1 (PCSK1)
- Leptin receptor (LEPR)/leptin hormone (LEP)
- Bardet-Biedl syndrome (BBS)
- Alström syndrome (AS)
- Smith-Magenis syndrome (SMS)
- SH2B Adaptor Protein 1 (SH2B1), including 16p11.2 deletion
- Nuclear receptor coactivator-1 (NCOA1), also referred to as steroid receptor coactivator 1 (SRC1)
- MC4R

Central melanocortin signaling is the central element of energy homeostasis (Holland 2019). Somewhat similar to patients with genetic variants in the MC4R pathway, in patients with hypothalamic lesions, leptin signaling is often disturbed and as a result melanocortin signaling is reduced (Enriori 2016; Roth 1998; Roth 2010; Patel 2002; Shaikh 2008). Imaging studies in humans and rodent models show that lesions of the ventromedial nucleus of the hypothalamus (VMN) and the region of the arcuate nucleus (ARC), are more often associated with hyperphagia and excessive weight gain (Ahmet 2006; DeVile 1996; Roth 2011; Daousi 2005; Holmer 2010; Elfers 2011).

Hypothalamic obesity (HO) is a form of severe obesity that arises from mechanical hypothalamic lesions/insults (e.g., tumors, tumor resections, radiotherapy treatment). Lesions of the hypothalamus can derive from various types of tumors (craniopharyngiomas, gliomas, pituitary adenomas, hamartomas) as well as from the surgeries and radiotherapies for the treatment of the tumor itself. Patients with HO display a higher degree of hyperleptinemia and hyperinsulinemia

when compared to individuals with normal body mass indexes (BMIs). Alpha-melanocortin stimulating hormone (α -MSH) can be detectable in blood, and its levels can change depending on different energy states (Enriori 2016); however, in patients with craniopharyngioma or post-surgical treatment for it, α -MSH levels are significantly reduced (Roth 2010; Roth 2011). Reduced serum α -MSH levels suggest melanocortin pathway deficiency, which might explain lower energy expenditure in peripheral tissues due to reduced fat and muscle fatty acid oxidation (Roth 2010; Roth 2011; An 2007).

In a rat model of "combined medial hypothalamic lesion" (CMHL rat model) for HO (Roth 2011), Roth et al found that the characteristic metabolic changes of human HO were recapitulated when the lesion included the rat ARC. In this rat model, α -MSH levels are reduced (Roth 2011), similar to patients with craniopharyngioma (Roth 2010).

Additionally, an MC3/4 receptor agonist, melanotan II (MTII) 1 mg/kg/day administered intraperitoneally over a period of 14 days, resulted in a robust reduction of weight gain in CMHL rats without rebound/tachyphylaxia (Roth 2012). Preclinical and clinical findings offer a rationale for a novel melanocortin treatment also in patients with HO to compensate for and potentiate defective leptin signaling.

Overall, nonclinical and clinical data demonstrate that setmelanotide restores normal hunger, satiety, and energy expenditure regulation, leading to profound reduction of excess weight, in essence as a form of "replacement therapy". Setmelanotide is authorized for marketing in the United States (US), Great Britain (GB), Israel, the European Union (EU), and Canada in adult and pediatric patients 6 years of age and older with obesity due to POMC, PCSK1, or LEPR (PPL) deficiency (USPI 2022; EU SmPC 2022; MHRA SmPC 2021; Israel PPI 2022; Product Monograph 2023). Additionally, setmelanotide is also approved in the US, EU, and Canada to treat chronic weight management in adult and pediatric patients 6 years of age or older with monogenic or syndromic obesity due to BBS (USPI 2022, SmPC 2022, Product Monograph 2023). The clinical testing and regulatory approval of setmelanotide in certain countries have established its therapeutic value. This trial will continue to explore the long-term safety and tolerability of setmelanotide in patients who have successfully completed a prior index trial of setmelanotide. Trial participation may continue for up to 7 years or until setmelanotide is otherwise available through authorized use, or unless there is not a clinically meaningful treatment effect.

Patients may enter this trial immediately upon completion of their index trial such that dosing of setmelanotide continues without gaps in therapy, if possible. Patients may also enter this trial from the extension phases of any prior index trial. Efforts should be made to have the last visit of a prior index trial or an index trial extension phase and the initial visit of this long-term extension trial occur on the same day, if possible.

An index trial is defined as any setmelanotide trial in which a patient participated prior to enrollment in this extension trial.

1.1. Setmelanotide Background and Clinical Experience

Setmelanotide is an 8-amino acid, cyclic peptide that binds with high affinity (inhibitory constant [Ki] = 2.1 nM) to the human MC4R and is efficient in activating MC4R (50% effective concentration $[EC_{50}] = 0.27 \text{ nM}$).

1.1.1. Clinical Background and Benefit–Risk Assessment

Nonclinical and clinical data generated to date with setmelanotide described in the Investigator Brochure (IB) provide meaningful information to support the benefit–risk assessment for the proposed use of setmelanotide in the current trial, a long-term extension trial for clinical evaluation of long-term treatment of obesity associated with genetic defects in the leptinmelanocortin pathway upstream of the MC4R and other abnormalities of the MC4R pathway.

The current clinical development program for setmelanotide is focused on rare monogenic forms of early-onset, severe obesity, including POMC deficiency obesity, LEPR deficiency obesity, and other genetic forms of early-onset, severe obesity with involvement of the leptin-MC4R pathway in their pathogenesis, including epigenetic obesity, PPL heterozygous obesity, and potentially other genetic and/or syndromic forms of obesity, and other abnormalities of the MC4R pathway, such as HO.

Informative clinical data from the initial phases of these trials in patients with early-onset severe obesity due to rare bi-allelic mutations in the *POMC* and *LEPR* genes, as well as BBS, are available and were published or presented at scientific meetings. The evolving profile of weight-related and hunger symptom reduction demonstrated with chronic setmelanotide treatment is important to consider, as these findings inform the overall benefit–risk consideration of setmelanotide.

In adult patients who tolerate the 3 mg QD dose level, if additional effect on

is desired in the current trial, a higher QD dose can be administered at the investigator's discretion and in consultation with the sponsor. The dose can be increased up to 4 mg QD, in patients with an absolute weight of >50 kg, and up to 5 mg QD in adult patients with an absolute weight of >60 kg. These dose levels have been investigated previously in trial RM-493-026. Adult patients exposed to these higher dose levels should be monitored closely via additional unscheduled visits or telephone calls to assess safety and tolerability. For patients who escalate to 4 or 5 mg QD, the dose level should be reduced to 3 mg and 4 mg if their absolute weight decreases to \leq 50 kg and \leq 60 kg, respectively. The maximum dose of setmelanotide is limited by absolute body weight (kg) in order to maintain exposure to excipients in the setmelanotide formulation at a lower level than those currently approved for other commercially available medicinal products (see Section 3.2 for further details).

Overall, the expected benefit–risk assessment supports continued evaluation of setmelanotide in these rare patient populations with high unmet medical needs.

Refer to the Investigator Brochure for data regarding setmelanotide administration at doses up to 5 mg.

2. TRIAL OBJECTIVES AND ENDPOINTS

2.1. Trial Objectives

2.1.1. Primary Objective

• To characterize safety and tolerability of setmelanotide in patients who have completed a previous trial on treatment with setmelanotide for obesity associated with

genetic defects upstream of the MC4R in the leptin-melanocortin pathway or with obesity related to other abnormalities in the MC4R pathway.

2.1.2. Exploratory Objectives

[figure not shown]

[figure not shown]
2.2. Trial Endpoints

2.2.1. Primary Endpoint

The safety and tolerability of setmelanotide, as assessed by the frequency and severity of AEs, as well as changes in physical examinations, vital signs, laboratory evaluations, and injection site reactions.

2.2.2.

3. INVESTIGATIONAL PLAN

3.1. Overall Design and Plan of the Trial

This is an extension trial of up to an additional 7 years duration for patients who have completed a previous trial of setmelanotide for rare genetic, syndromic, or acquired diseases of obesity upstream of the MC4R in the melanocortin-leptin pathway and other abnormalities of the MC4R pathway. Since continued assessments of the safety and efficacy of setmelanotide are the same in this extension trial regardless of the disease studied in the index trial, all patients can be followed

in this single extension trial. Nevertheless, the analysis of each sub-population will be performed separately with the ability to combine data from the original index trial and this extension trial on a disease-specific basis.

For patients who qualify and provide consent, the trial will start immediately on the completion of their index protocol such that there are no gaps in treatment, if possible. Efforts should be made to have the last visit of a prior index trial or an index trial extension phase and the initial visit of this long-term extension trial to occur on the same day, if possible.

Patients will be assessed in the clinic approximately every 3 months for vital signs, AEs, concomitant medications, height (in children),

Safety laboratory samples will be collected at each visit and additional assessments will be done on a yearly basis. In general assessments will be less frequent and burdensome than was required in their index protocol.

Unscheduled clinic and/or telephone visits may be added at the discretion of the investigator to follow any changes in dose or adverse event, as required.

3.2.1. Rationale for Setmelanotide Administration at Doses Up to 5 mg

While the target dose of setmelanotide is 3 mg QD, nonclinical and clinical data support dose escalation up to 5 mg QD in adult patients in this trial. For additional information, see Section 5.2.1 and the IB.

Refer to the IB for additional information.

3.3. Patient, Cohort or Trial Termination

A specific gene cohort (or gene variants or subset of variants) or the whole trial may be terminated, if in the opinion of the investigator (at a participating site) or the sponsor there is sufficiently reasonable cause. The terminating party will provide written notification. documenting the reason for trial termination to either the investigator or the sponsor.

Circumstances that may warrant termination include, but are not limited to:

- Determination of unexpected, significant, or unacceptable risk to patients.
- Failure to enter patients at an acceptable rate.
- Insufficient adherence to protocol requirements.
- Insufficient complete and/or evaluable data.
- Plans to modify, suspend or discontinue the development of the study drug.
- Lack of clinical efficacy.

Should the trial be closed prematurely, all trial materials must be returned to the sponsor or designee.

3.4. Transition into Another Rhythm Trial

Patients enrolled in this extension trial may exit the trial to participate in other setmelanotide clinical trials with the patient's (or legal guardian's) written informed consent, at the discretion of the investigator and sponsor. The patient is to complete the extension Transition Visit prior to commencing treatment in the other setmelanotide clinical trial; applicable data from this visit will serve as Screening data for the other trial. After completion of the Transition Visit, the patient will not need to complete the Early Termination (ET) visit in the extension trial prior to transition to the other trial.

At the conclusion of the other setmelanotide trial, the patient may transition back into this extension trial, again with the patient's written informed consent, at the discretion of the investigator and sponsor, if continuation of setmelanotide treatment is considered beneficial and the patient continues to be eligible for the extension trial. In such cases, the patient will resume the extension trial at the time point/visit at which he or she was at prior to transition to the other trial. Furthermore, after transition back into this extension trial, the patient is to receive setmelanotide at the same dose as they had received prior to transition to the other trial, unless the dose needs to be reduced due to tolerability reasons or in case a dose increased is required for potential additional efficacy needs, at the investigator's discretion. If at the time the patient completes the other setmelanotide trial, setmelanotide becomes commercially available for an indication for which that patient qualifies, the patient will not be eligible to re-enter this extension trial.

If a patient transitions to another setmelanotide clinical trial before completing the ET visit in this extension trial, but does not transition back into this extension trial, the patient will not complete the ET visit or follow-up in the extension trial.

If feasible, patients are to have no interruption in setmelanotide treatment between this extension trial and the other setmelanotide trial. If an interruption in treatment is necessary due to administrative reasons, every effort is to be made to minimize the duration of the interruption and interruptions >21 days are not permissible without prior approval from the sponsor.

If a patient in this extension trial elects to transition to another setmelanotide clinical trial, then any screening assessments performed as part of the Screening visit in the other setmelanotide clinical trial within 30 days of the Transition Visit in this extension trial need not be repeated.

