1.2.2. Exploratory Objectives

1.3. Study Design

1.3.1. Synopsis of Study Design

This is a long-term extension study of up to an additional 7 years duration beyond the index trial for patients who have completed a previous study on treatment with setmelanotide for rare

genetic, syndromic, or acquired diseases of obesity upstream of the MC4R in the melanocortinleptin pathway and other abnormalities of the MC4R pathway.

Since continued assessments of the safety and efficacy of setmelanotide are the same in this extension protocol regardless of the index protocol, all patients can be followed consistently in this single extension protocol. The index trials relevant to this study are identified in Table 1-1. Eligible and consenting patients start in the extension trial immediately on the completion of their index protocol (ideally, Visit 1 of this trial will coincide with the final visit of the index trial) in order to limit gaps in treatment.

Patients are assessed approximately every 3 months for adverse events (AEs), concomitant medications, the height (in children),

Patients enrolled in this extension trial may exit the trial to participate in other setmelanotide clinical trials. At the conclusion of the other setmelanotide trial, the patient may transition back into this extension trial. In such cases, the patient resumes the extension trial at the time point/visit at which he or she was at prior to transition to the other trial. Furthermore, after transition back into this extension trial, the patient receives setmelanotide at the same dose as they had received prior to transition to the other trial, unless the dose needs to be reduced due to tolerability reasons or in cases where a dose increase is required for potential additional efficacy needs at the investigator's discretion.

Study Identifier	Study Phase	Number of Subjects who participated in Extension Trial	Diagnosis of Subjects
011	2	9	Genetic disorder of obesity
012	3	13	Early Onset POMC/PCSK1 Deficiency Obesity
014	2	119	Genetic disorder of obesity
015	3	12	LEPR Deficiency Obesity
023	3	38	BBS and AS
030	2	14	Hypothalamic Obesity
034	2	1	Genetic disorder of obesity

Table 1-1Index Studies Currently Included in RM-493-022

Abbreviations: AS=Alstrom Syndrome; BBS= Bardet-Biedl Syndrome; LEPR = Leptin Receptor; POMC = Pro-opiomelanocortin.

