Note: Patients in RM-493-037 were previously enrolled in one of the index studies and RM-493-022 prior to entering the RM-493-037; patients were eligible to reenroll in RM-493-022 after participation in the RM-493-037. These patients are analyzed according to their index trial.

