3.4. Baseline Definitions

To assess the temporal dynamics of setmelanotide on weight, BMI, BMI z-score, percent of BMI 95th percentile, waist circumference, body composition, two baseline definitions will be utilized:

- Extension study baseline will be defined as the last value obtained in the index study prior to the first dose of active treatment in the extension study. For subjects with a >1 day gap in Setmelanotide treatment between the index study and the extension study, the last value obtained prior to first active treatment dose in the extension study will be used as the baseline
- Index study baseline will be defined as the last value obtained prior to the first dose of active treatment in the index study.

For all other parameters, baseline will use the extension study baseline as defined above.

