3.12. Visit Windows

It is expected that all visits should occur according to the protocol schedule. All data will be tabulated per the evaluation visit as recorded on the CRF even if the assessment is outside of the visit window. If the evaluation visit is missing in the database but there are data from an unscheduled or additional visit that is inside the visit window, the data from the unscheduled or additional visit will be used in data summaries. All available data will be listed for each subject.

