4.5.10. Vital Signs

Vital signs will be measured as shown in the SOA (Table 1-2). Aside from those used in exploratory evaluation, the raw, change and percent change from extension study baseline of additional vital signs of temperature, heart rate, systolic blood pressure, diastolic blood pressure, respiratory rate will be summarized descriptively by visit. A by-subject listing of all vital signs will be provided.

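### Patients who leave for another setmelanotide trial and return keep their old visit number, so the by-visit safety tables date their later values too early by the full time away

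*Protocol*

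**What the plan says.** Protocol 3.4 lets a patient leave for another setmelanotide trial and later come back. On return, "the patient will resume the extension trial at the time point/visit at which he or she was at prior to transition". SAP 1.3.1 repeats the rule: "the patient resumes the extension trial at the time point/visit at which he or she was at prior to transition to the other trial". Where feasible, treatment is not to be interrupted between the two trials, and a gap of more than 21 days needs the sponsor's prior approval.

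SAP 3.12 sets the time axis for the tables: "All data will be tabulated per the evaluation visit as recorded on the CRF even if the assessment is outside of the visit window". Its one exception lets an unscheduled visit inside the window stand in for a missing scheduled one.

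The note to SAP Table 1-1 shows that return is foreseen. RM-493-037 patients had been in this extension first, and "patients were eligible to reenroll in RM-493-022 after participation in the RM-493-037". On how to analyse them it says only: "These patients are analyzed according to their index trial". That fixes their group but not their position in time.

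The extension baseline in SAP 3.4 is "the last value obtained in the index study prior to the first dose of active treatment in the extension study", with a variant for a treatment gap at entry. No new baseline on return is mentioned.

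**The concern.** The visit number stands still while the patient is elsewhere, but the calendar and, normally, treatment go on. Five sets of safety tables are arranged by visit: injection sites (SAP 4.5.3), laboratory shifts (4.5.4), ECG shifts (4.5.6), vital signs (4.5.10, where results up to "respiratory rate will be summarized descriptively by visit") and physical examination shifts (4.5.11). In each, one column can mix patients seen on schedule with returners seen many months later. A late change in blood pressure or in a laboratory grade would then appear as an earlier one.

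This matters because the trial's purpose is long-term safety, and Protocol 8.4 says laboratory and vital sign data will be summarised according to when they were collected. No passage that can be read in either document corrects the axis for returners.

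**Working it through.** The plan states no figure to reproduce. The check is date arithmetic on the schedule of assessments (Protocol Table 1, repeated as SAP Table 1-2).

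**Inputs from the documents**
- Nominal start weeks: V5 = 53, V6 = 65, V7 = 77, V9 = 104, V10 = 116, V11 = 128, V13 = 156, V29 = 356.
- Extension exposure (SAP 4.5.1): last extension dose date minus first extension dose date, plus 1. Time in another trial is not subtracted.
- Subjects in SAP Table 1-1: 9 + 13 + 119 + 12 + 38 + 14 + 1 = 206.

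**Assumptions**
- Time away is 13, 26 or 52 weeks.
- The patient is otherwise on schedule, and the interval to the next visit runs its normal length after return.
- First extension dose means the original one.

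**Formulas**
- True week = labelled week + weeks away.
- Exposure in days at a resumed V9 = (103 + weeks away) × 7 + 1. With no absence this is 103 × 7 + 1 = 722 days, the value that the week-104 label implies.

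| Weeks away (assumed) | True week at label V5 (53) | Nearest scheduled visit | True week at label V9 (104) | Nearest scheduled visit | Lag in visits | Exposure at V9 (days) |
|---|---|---|---|---|---|---|
| 13 | 66 | V6 (65) | 117 | V10 (116) | 1 | 813 |
| 26 | 79 | V7 (77) | 130 | V11 (128) | 2 | 904 |
| 52 | 105 | V9 (104) | 156 | V13 (156) | 4 | 1086 |

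The lag carries forward to all of that patient's later visits. The exposure column shows the second inconsistency. After an assumed 52 weeks away, the exposure table would credit 1086 days to a patient whose vital signs sit in a column implying 722, a difference of 364 days. Follow-up since the extension baseline (SAP 4.1) also reads as calendar time and so departs from the labels in the same way.

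**Share of patients.** The number of returners is unknown. For scale only, 5, 12 or 20 returners would be 2.4%, 5.8% or 9.7% of 206. The share in any one column would be larger if fewer patients attend that visit.

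**The case against.** The best defence is that the visit number measures time within this protocol, by stated design. It never measured cumulative exposure, since patients arrive from index trials of different kinds, some of them double-blind. The main adverse event summaries (SAP 4.5.2) are incidences by system organ class and preferred term and do not use visit number. Listings carry relative study day (SAP 3.2), and the whole analysis is descriptive. All of this stands, and it confines the point to the by-visit safety tables. It does not remove the point, because the SAP uses calendar time for exposure and follow-up, and Protocol 8.4 ties the safety summaries to time of collection.

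A reader might infer more than the documents support:
- **That misplaced data already exist.** The note to SAP Table 1-1 establishes that RM-493-037 patients could return, not that any did or how many.
- **That weight regain or maintenance of effect is misdated.** SAP 4.3 is almost wholly redacted, so the placing of those data in time cannot be judged.
- **That late visits lose returners' data.** A returner still passes through the later labels in turn. Those columns receive the data, only collected later than labelled.
- **That each returner has two records at one visit.** The resumption wording could mean repeating the last visit or taking the next one, and the Transition Visit has its own column. If a visit is repeated, SAP 3.12 has no rule for choosing between the records.
- **That post-return data should simply move to the nearest nominal visit.** After an assumed 52 weeks away, V25 to V29 would fall at weeks 360, 372, 384, 396 and 408, all nearest V29 (week 356). After 26 weeks, V27 to V29 (358, 370, 382) would collapse in the same way, and the V9 ECG at week 130 would move to V11, where no ECG is scheduled.

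**Conclusion.** The point holds for the by-visit safety tables. Read together, Protocol 3.4, SAP 1.3.1 and SAP 3.12 place a returner's values earlier than their true time since the first extension dose, by the full length of the absence. The same labels conflict with SAP 4.5.1 and 4.1. Under the assumed 26 to 52 weeks away, this is 2 to 4 scheduled visits.

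The mechanism is certain from the text, but its effect on any table is not, because neither the number of returners nor the time away is given. The effect could be negligible. It merits correction before the final analysis because the trial describes safety over years and the remedy is cheap. It does not call the overall adverse event incidence or the listings into question.

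**What to change.** Add a rule to SAP 3.12 for patients who transition out and return:
1. Report how many returned and how long each was away.
2. Flag post-return records, keeping the CRF visit label in listings.
3. Repeat the by-visit safety tables with returners' data cut at the Transition Visit.
4. Summarise post-return safety values separately by actual time since the original first extension dose, for example in yearly bins. Include an open-ended bin beyond week 356 and a stated rule for choosing one record per bin. Do not re-map to the nearest nominal visit.
5. State that, for returners, first dose (hence relative study day and exposure) means the original first extension dose, and that baseline is not reset on return, if that is the intention.

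The cost is SAP wording, one derivation from dates already collected and a few extra tables. Sites do nothing new. The drawback is that post-return values in the separate summary will not line up with CRF visit labels.
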